### CHOICE Protocol V2.0, 08.02.2024 Based on protocol template v1.0 11/10/2019

Procedures	Screening/ Baseline*	Randomi sation (within 6 weeks of consent)	CHOICE Intervention Visit	ENCOUR AGE Sub- study 6 months (+/- 1 month) (optiona I - must consent)	12 months (+/- 3 months)	24 months (+/- 3 months)	Study Completion
Signed Consent Form (including collection of contact details) 	х						
Assessment of Eligibility Criteria	Х						
Demographic information	Х						
Socio-economic data,	Х						
Baseline dental assessment (Dentist) 	Х						
Oral Health Behaviours and Regret/Relief Questionnaire 	X**				х	Х	
Parental-Caregiver Perceptions Questionnaire 	X**				х	Х	
EQ-5D-Y Proxy Questionnaire 	X**				Х	Х	
Randomisation		Х					
Delivery of CHOICE intervention to child's parent/primary caregiver			X***				
Participants goals and prescription for change 			X***				
Audio recordings of CHOICE intervention			X***				
CHOICE intervention feedback and Regret/Relief Surveys 			X***				
Qualitative Interviews****					Х	Х	
Safety data assessment			Х		Х	Х	
Final dental assessment (Blinded Assessor) 						Х	
Dental treatment and dental pain data recorded from patient records by GDP 					х	Х	
Dental treatment data requested from NHS 							Х
ENCOURAGE saliva sample (optional – must consent)		X****		X*****			

\*At baseline, informed consent must be in place prior to any procedures occurring

\*\* The questionnaires at Screening/Baseline may be collected at a subsequent visit where randomisation and the intervention visit occurs as long as they are completed prior to randomisation.

\*\*\*For those allocated the intervention, this must be completed within 12 weeks of randomisation. These activities can occur on the same day as randomisation

\*\*\*\* Qualitative interviews will be carried out 6-12 months following intervention

Child data collection

Parent/Primary caregiver data collection

\*\*\*\*\* ENCOURAGE saliva samples will be collected at Randomisation visit and 6 months (+/- 1 month) from randomisation. This is an optional sub-study.

Participant follow-up will occur 12 months (+/- 3 months) and 24 months (+/- 3 months) following randomisation. Parents/primary caregivers of participants assigned to the Intervention Group will have a trial visit to receive the intervention within 6 weeks of randomisation

At 12 months (+/- 3 months) post randomisation, the dental records will be reviewed to complete the following:

- Dental treatment and dental pain data recorded during the last 12 months
- Safety Data Assessment during the last 12 months

At 24 months (+/- 3 months) post randomisation, the dental records will be reviewed to complete the following:

- Dental treatment and dental pain data recorded during the last 12 months.
- Safety Data Assessment during the last 12 months.

Safety data can be collected as part of the study questionnaires.

A dental assessment will also be completed by a blinded assessor at 24 months (+/- 3 months).

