# 6.2 Outcomes

Outcome	Timing of measurement	Method of measurement	Objective	
Primary outcome	Primary outcome			
Caries experience (measured at dentinal level) at 24 months post- randomisation in any tooth which was caries free or unerupted at baseline	Baseline and 24 months (+/-3 months post randomisation).	Dental status examination to national standards as used in UK Dental Epidemiology Surveys of Child Dental Health	1, 8, 10, 11	
Secondary outcome(s)				
Number of teeth (caries free or unerupted at baseline) with caries experience into dentine 24 months post-randomisation.	Baseline and 24 months (+/-3 months post randomisation).	Dental status examination to national standards as used in UK Dental Epidemiology Surveys of Child Dental Health	2, 8	

 
Parent reported attitudes to child oral health behaviours (seven subscales)
 
Parental efficacy in relation to child toothbrushing
 
Importance and intention to brush child's teeth
 
Parental efficacy in relation to controlling child sugar snacking
 
	Baseline, 12 months and 24 months (+/- 3 months post randomisation).	Parent reported Oral Health Behaviours and Regret/Relief Questionnaire (OHB-RRQ)	2,8, 10, 11	

 
Importance and intention to control child sugar snacking
 
Perceived seriousness of tooth decay in children
 
Chance control – decay occurs by chance
 
Regret/Relief regarding child oral health behaviours
 
			

 
Parent reported child oral health behaviours (four measures)
 
Level of toothbrushing
 
Sweets consumption
 
Sugary drinks consumption
 
Dental attendance
 
	Baseline, 12 months and 24 months (+/- 3 months post randomisation).	Parent reported Oral Health Behaviours and Regret/Relief Questionnaire (OHB-RRQ)	2, 8
Episodes of dental pain	12 months and 24 months (+/- 3 months post randomisation).	From child dental treatment records of episodes of dental pain.	2
Number of filled teeth (caries free or unerupted at baseline) 24 months post randomisation	Baseline and 24 months (+/-3 months post randomisation).	Dental status examination to national standards as used in UK Dental Epidemiology Surveys of Child	2
Number of extracted teeth (caries free or unerupted at baseline) 24 months post randomisation	Baseline and 24 months (+/- 3 months post randomisation).	Dental status examination to national standards as used in UK Dental Epidemiology Surveys of Child	2
Economic outcomes			

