### 10.8.3 Efficacy Assessments

The primary outcome, the efficacy assessment, is measured 24 months post-randomisation (+/- 3 months), and is the development of caries in any tooth which was caries free or unerupted at baseline. Caries is measured at the dentinal level of involvement (Pitts et al., 1997). Children will be examined supine with a single-use plane mouth mirror, and teeth will be illuminated by a portable Daray light of 2,000 lux. The presence of upper anterior buccal plaque will be recorded as an indicator of oral cleanliness. Teeth will be examined for untreated caries into dentine, restorations, and fissure sealants. (Pitts et al., 1997) Cotton wool rolls will be used to dry teeth, and probes will be available to remove debris and to check the integrity of restorations and the presence of sealants. Examining procedures are those set by the national dental epidemiology programme under which children are examined in school using mobile equipment (Public Health England, 2021). Assessments will be conducted in the child's dental practice, where possible, or in the child's school or if requested by parent, at the child's home. All dental assessments will be blind to group assignment. Organisation of the timetable for the clinical assessments including contacting practices, schools and families will be undertaken by the CHOICE central research team based at Queen's University Belfast.

All dental treatment that is provided will be recorded by the participants' general dental practitioner (GDP) during the trial period. At the time of final assessment, dental records will be examined of the trial participants by the GDP to capture all the dental treatment and reported dental pain. Hospital records of dental extractions will also be recorded. Where consent has been provided, administrative records will be used for the study period for any siblings (aged up to 11 years on study entry) residing with the participant and attending the same dental practice to assess their dental treatment.

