### 10.8.8 Health Economic Assessments

Utilization of care will be taken from clinical records and monetised using the Northern Ireland Statement of Dental Remuneration for care provided by the GDP and from National Cost Collections for hospital provided extractions. These costs will be aggregated over the 24-month study period in the base case analysis (and over 10 years in the follow-up study). To these will be added the cost of the intervention for the intervention group. Intervention costs will be based on nurse delivery time as recorded by the providing nurse and monetised using agenda for change pay rates for a dental nurse at band 2 in the base case analysis. As a validation exercise a random sample of intervention delivery times will be timed by the research team and compared with those reported by nurse providers. Incremental costs in the base case analysis will be based on differences in costs over 24 months between the control and intervention group. As a range of outcomes are captured in the study including the proportion who accumulate additional caries, the number of fillings provided, episodes of pain and quality of life (QOL) measures, a range of incremental effects will also be calculated based on differences in these at 24 months. Where appropriate, for example in respect of quality of life, incremental effects will be based on differences in the change in QOL between baseline and follow-up between intervention and control groups.

Mean differences in cumulative discounted costs and effects between the intervention and control groups will be described and tested using standard parametric approaches to examine differences in mean costs, proportion of children whose caries progress, episodes of pain, fillings and health-related quality of life etc. A series of incremental

cost effectiveness ratios will be estimated detailing the difference in cost divided by the difference in effect between intervention and control groups. To take account of the possibility that costs, and effects are jointly distributed, uncertainty around ICERs will be explored in deterministic models using a nonparametric bootstrapping approach and uncertainty around the willingness to pay for outcomes using cost effectiveness acceptability curves.

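### Both record reviews look back a fixed 12 months from dates that may move by 3 months either way, so dental pain episodes can be missed, covered twice or taken from before randomisation

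*Protocol*

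**What the plan says.** The text after the schedule table in Protocol Section 10.8 sets two reviews of the dental records. The first reads "At 12 months (+/- 3 months) post randomisation, the dental records will be reviewed to complete the following", and the second "At 24 months (+/- 3 months) post randomisation, the dental records will be reviewed to complete the following". Both then list the same two items: "Dental treatment and dental pain data recorded during the last 12 months" and "Safety Data Assessment during the last 12 months". Neither look-back is tied to randomisation or to the previous review.

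Section 10.8.3 words the final review differently. The general dental practitioner (GDP) records all treatment given during the trial, and at the final assessment "dental records will be examined of the trial participants by the GDP to capture all the dental treatment and reported dental pain". No 12-month limit appears there.

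Three other places bear on what is affected:

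- **Outcomes table (Section 6.2).** The secondary outcome of dental pain episodes, timed at 12 and 24 months, is taken "From child dental treatment records of episodes of dental pain". The caries outcomes and the filled and extracted teeth come from the dental examination.
- **Economics (Sections 10.8.8 and 13.7).** Section 10.8.8 takes use of care from clinical records and says "These costs will be aggregated over the 24-month study period in the base case analysis". It also lists pain episodes among the incremental effects. Section 13.7 takes treatment resource use from administrative claims data covering the 24 months.
- **Safety (Sections 10.8.6, 12.6 and 12.9.1).** Safety events are monitored from randomisation to the final examination, and related serious adverse events are reported within 24 hours of the site becoming aware.

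**The concern.** Two 12-month windows join end to end only if the reviews are 12 months apart, and they start at randomisation only if the first review is at month 12. The protocol allows the first review anywhere from month 9 to 15 and the second from month 21 to 27. A practice that follows Section 10.8 to the letter, entirely within protocol, can therefore leave part of follow-up unread, read part of it twice, or include time before the child was randomised.

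The pre-randomisation part matters because of how children enter. They are recruited with a lesion already present, families may be approached at a dental appointment (Section 10.2), and randomisation follows consent by at most 6 weeks (Section 10.5.1). A first review at month 10.5 or earlier looks back at least 1.5 months before randomisation, and so always reaches consent. Pain or treatment around recruitment could then be recorded as an outcome. Such events cannot depend on allocation, so counting them pulls a comparison of rates towards no difference.

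An analysis plan cannot repair this fully. It can remove duplicates if dates are held, but it cannot recover events that practices were not asked to extract.

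**Working it through.** The protocol states no figure for coverage, so there is none to reproduce. The check is interval arithmetic on its own dates.

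**Inputs (all Section 10.8).** First review at t1, from 9 to 15 months after randomisation. Second review at t2, from 21 to 27 months. Look-back of 12 months at each.

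**Windows.** Review 1 covers t1 − 12 to t1. Review 2 covers t2 − 12 to t2.

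**Formulas.**

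- Missed at the start: max(0, t1 − 12)
- Gap between the windows: max(0, t2 − 12 − t1)
- Covered twice: max(0, t1 − (t2 − 12))
- Pre-randomisation time included: max(0, 12 − t1)

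Missed time below is start plus gap. Time after the second review is not counted as missed, because it follows from the visit window and not from the look-back.

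| t1 / t2 | Review 1 covers | Review 2 covers | Missed | Covered twice | Pre-randomisation |
|---|---|---|---|---|---|
| 9 / 21 | −3 to 9 | 9 to 21 | 0 | 0 | 3 |
| 9 / 24 | −3 to 9 | 12 to 24 | 3 | 0 | 3 |
| 9 / 27 | −3 to 9 | 15 to 27 | 6 | 0 | 3 |
| 12 / 21 | 0 to 12 | 9 to 21 | 0 | 3 | 0 |
| 12 / 24 | 0 to 12 | 12 to 24 | 0 | 0 | 0 |
| 12 / 27 | 0 to 12 | 15 to 27 | 3 | 0 | 0 |
| 15 / 21 | 3 to 15 | 9 to 21 | 3 | 6 | 0 |
| 15 / 24 | 3 to 15 | 12 to 24 | 3 | 3 | 0 |
| 15 / 27 | 3 to 15 | 15 to 27 | 3 | 0 | 0 |

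Only 12 / 24 is zero throughout. This holds for every pair of dates, not just those listed: no missed start and no pre-randomisation time requires t1 = 12, and no gap and no overlap then requires t2 = 24. Over a fine grid of both windows the maxima are 6 months missed, 6 months covered twice and 3 months pre-randomisation.

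**Average, under an assumption.** The protocol does not say how review dates fall within their windows. If they were independent and uniform:

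- Missed start: (3²/2)/6 = 0.75 month. Pre-randomisation time is the same by symmetry, 0.75 month.
- The gap and the overlap are the positive and negative parts of the difference between two uniform variables of width 6. Each has mean 6/6 = 1.0 month.
- Total missed: 0.75 + 1.0 = 1.75 months.

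A simulation of one million pairs gave 1.750 months missed and 1.000 month covered twice. Dates bunched near 12 and 24 months would give less.

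**After the change.** With review 1 covering 0 to t1 and review 2 covering the day after t1 to t2, all four quantities are zero for every permitted pair.

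**The case against.** The strongest reply is that Section 10.8.3 already asks for everything. A practice that follows it at the final review closes any gap, and the 12-month wording may simply be shorthand for year 1 and year 2. That is a fair reading of intent, and it means loss of events is not certain. It does not settle the matter, because Section 10.8 limits the same 24-month review to 12 months and nothing says which rule prevails. A practice following Section 10.8.3 would also extract again what the first review took, and the protocol gives no rule for removing duplicates. With up to 40 practices, both readings could be in use.

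Other parts of the reply stand:

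- **Safety.** A reader might infer that safety events are lost or duplicated. The documents do not support this. Only related serious adverse events are reportable, monitoring is continuous, and reporting runs from awareness. The look-back weakens only the record check as a backstop.
- **Costs.** A reader might infer that the base-case treatment cost is wrong. Section 13.7 draws on claims data for the full 24 months, which the look-back does not touch. The cost is exposed only if the clinical records named in Section 10.8.8 are the source used.
- **Double counting.** Time covered twice becomes events counted twice only if events are undated or not de-duplicated. The case report form is not shown.
- **Bias between arms.** Both arms share the schedule, and randomisation is stratified by site. Nothing shows that review timing differs by arm.

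**Conclusion.** The point holds for dental pain. Followed as written, the look-back in Section 10.8 mis-measures a named secondary outcome that is also an effect measure in the economic analysis and has no other source in the protocol. It also conflicts with Section 10.8.3.

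The arithmetic maxima rest only on the protocol's windows. They are extremes, reached when the two reviews fall at opposite limits, and a reader should not take 6 months as typical. The averages rest on uniform, independent dates, which the protocol does not state. The missed, twice-covered and pre-randomisation months are different kinds of error and should not be added into one figure of lost follow-up.

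The expected effect is a less accurate count, with some dilution where pre-randomisation events enter. A systematic difference between arms is not shown. The primary outcome, the number of carious teeth, and the filled and extracted teeth are unaffected.

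**What to change.** Reconcile Sections 10.8 and 10.8.3 as follows:

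- **First review:** from the date of randomisation to the date of the review.
- **Second review:** from the day after the first review to the 24-month assessment.
- **Event dates:** record a date for each treatment and pain episode, so that pre-randomisation and duplicate entries can be excluded.
- **Safety record check:** use the same two periods.
- **Section 10.8.3:** state that complete capture is reached by the two reviews together.

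Follow-up would still end between months 21 and 27 because of the visit window. Allowing for that is a matter for the analysis plan.

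The cost is small: the look-back lines in Section 10.8, a matching sentence in Section 10.8.3, and the prompt on the case report form. No visit is added. It is best done before reviews are completed, since going back to the records later takes more work.

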### 10.8.1 Method of Contact

At 12 months (+/- 3 months) and 24 months (+/- 3 months) post randomisation, parents/primary care-givers will be sent a link to complete the study questionnaires required at these time points. If these are not completed, parents/primary caregivers may be contacted by telephone or post to enhance completion. A password protected keeping in touch website developed by Parenting NI will be made available to participants. This will involve comprehensible information about the trial that is publicly available and prompts for continued involvement.

### 10.8.2 Safeguarding

If a safeguarding issue were to arise that warranted a confidentiality breach and a referral to other services such as the Police/GP/Social Services during the course of the research activities, the dental teams will follow usual safeguarding processes as appropriate within their dental setting.

### 10.8.3 Efficacy Assessments

The primary outcome, the efficacy assessment, is measured 24 months post-randomisation (+/- 3 months), and is the development of caries in any tooth which was caries free or unerupted at baseline. Caries is measured at the dentinal level of involvement (Pitts et al., 1997). Children will be examined supine with a single-use plane mouth mirror, and teeth will be illuminated by a portable Daray light of 2,000 lux. The presence of upper anterior buccal plaque will be recorded as an indicator of oral cleanliness. Teeth will be examined for untreated caries into dentine, restorations, and fissure sealants. (Pitts et al., 1997) Cotton wool rolls will be used to dry teeth, and probes will be available to remove debris and to check the integrity of restorations and the presence of sealants. Examining procedures are those set by the national dental epidemiology programme under which children are examined in school using mobile equipment (Public Health England, 2021). Assessments will be conducted in the child's dental practice, where possible, or in the child's school or if requested by parent, at the child's home. All dental assessments will be blind to group assignment. Organisation of the timetable for the clinical assessments including contacting practices, schools and families will be undertaken by the CHOICE central research team based at Queen's University Belfast.

All dental treatment that is provided will be recorded by the participants' general dental practitioner (GDP) during the trial period. At the time of final assessment, dental records will be examined of the trial participants by the GDP to capture all the dental treatment and reported dental pain. Hospital records of dental extractions will also be recorded. Where consent has been provided, administrative records will be used for the study period for any siblings (aged up to 11 years on study entry) residing with the participant and attending the same dental practice to assess their dental treatment.

### 10.8.4 Process Evaluation

Mechanisms of impact will be investigated via qualitative interviews with up to 40 parents/primary caregivers 6-12 months after receiving the CHOICE intervention. An interview schedule will be developed to assess how the

intervention activities and participants' interactions trigger reported change in toothbrushing and sugar behaviours, maintenance of any behaviour change, automaticity, self-efficacy, intrinsic motivation, relief/regret and any unintended effects. Interviews will be conducted online/over the phone and audio-recorded for transcription and subsequent analysis.

Fidelity to the CHOICE intervention will be assessed from audio-recordings routinely undertaken as a part of the delivery of the intervention.

### 10.8.5 Implementation

Barriers and facilitators to routinely integrating DR-BNI into general dental practice will be explored from the Theoretical Domains Framework (TDF) perspective (Atkins et al., 2017) as well as speaking with the principal investigators at each site (dental practices) to capture usual preventive care for children. This will be undertaken by focus groups/interviews with key PPI stakeholders including parents/primary caregivers and the dental team. An interview schedule for each group will be developed guided by the TDF and data will be analysed using framework analysis (Gale et al., 2013). These will take place between 24-36 months from the start of the trial. Interviews will be conducted online/over the phone and audio-recorded for transcription and subsequent analysis.

### 10.8.6 Safety Assessments

Active monitoring of safety events experienced by trial participants will take place from randomisation until 24 months (+/- 3 months) post randomisation. Reportable safety events will include:

• A serious adverse event related to the trial procedures or intervention

## 10.8.7 Quality of Life Assessments

EQ-5D-Y questionnaire will be completed by parent/primary caregiver participants at Baseline, 12 month and 24 month follow-up.

### 10.8.8 Health Economic Assessments

Utilization of care will be taken from clinical records and monetised using the Northern Ireland Statement of Dental Remuneration for care provided by the GDP and from National Cost Collections for hospital provided extractions. These costs will be aggregated over the 24-month study period in the base case analysis (and over 10 years in the follow-up study). To these will be added the cost of the intervention for the intervention group. Intervention costs will be based on nurse delivery time as recorded by the providing nurse and monetised using agenda for change pay rates for a dental nurse at band 2 in the base case analysis. As a validation exercise a random sample of intervention delivery times will be timed by the research team and compared with those reported by nurse providers. Incremental costs in the base case analysis will be based on differences in costs over 24 months between the control and intervention group. As a range of outcomes are captured in the study including the proportion who accumulate additional caries, the number of fillings provided, episodes of pain and quality of life (QOL) measures, a range of incremental effects will also be calculated based on differences in these at 24 months. Where appropriate, for example in respect of quality of life, incremental effects will be based on differences in the change in QOL between baseline and follow-up between intervention and control groups.

Mean differences in cumulative discounted costs and effects between the intervention and control groups will be described and tested using standard parametric approaches to examine differences in mean costs, proportion of children whose caries progress, episodes of pain, fillings and health-related quality of life etc. A series of incremental

cost effectiveness ratios will be estimated detailing the difference in cost divided by the difference in effect between intervention and control groups. To take account of the possibility that costs, and effects are jointly distributed, uncertainty around ICERs will be explored in deterministic models using a nonparametric bootstrapping approach and uncertainty around the willingness to pay for outcomes using cost effectiveness acceptability curves.

A discount rate of 1.5% will be used in the base case analysis based on the intervention being construed to be a public health intervention. Missing data will be imputed using multiple imputation methods. An intention to treat approach will be adopted for analyses. Given observed disparities in oral health and use of dental services related to socio-economic status (SES) we plan to undertake sub-group analysis related to socio-economic status and ethnicity. Should significant differences in cost-effectiveness exist, the samples will be re-weighted to adjust for differences in SES and incremental cost-effectiveness re-estimated. As an additional check, a seemingly unrelated regression approach will be used to estimate ICERs and models adjusted and unadjusted for SES reported. This approach will be repeated with respect to ethnicity.

A series of sensitivity analyses will be undertaken. Individual parameter values will be varied in a series on one way sensitivity analyses that include unit costs, discount rates and time taken to deliver the intervention. Spill-over effects related to sibling effects will be added to those experienced by the index based on observed differences in use of dental care and the relationships between use of dental care and QOL observed from the literature and observed in the study. (How for example QOL varies with additional fillings and extractions,) A probabilistic sensitivity analysis will be used to examine the sensitivity of results to joint variations in input parameters.

